3.2 Secondary Objectives

The secondary objectives of this study are:

- Compare the total time, in minutes, during the first 24 hours that the patient achieves target HR (HR < 110 bpm) between patients who receive a repeated amiodarone bolus dosing regimen and those who receive a conventional amiodarone bolus dosing regimen.
- Compare the time to achieve target HR (HR < 110 bpm) between patients who receive a repeated amiodarone bolus dosing regimen and those who receive a conventional amiodarone bolus dosing regimen.

- Compare the time to achieve NSR between patients who receive a repeated amiodarone bolus dosing regimen and those who receive a conventional amiodarone bolus dosing regimen.
- Compare the percentage of patients who achieve NSR by ICU discharge and hospital discharge between patients who receive a repeated amiodarone bolus dosing regimen and those who receive a conventional amiodarone bolus dosing regimen.
- Compare the percentage of patients who have recurrent AF before ICU discharge and before hospital discharge between who patients who receive a repeated amiodarone bolus dosing regimen and those who receive a conventional amiodarone bolus dosing regimen.
- Compare the incidence and severity of hypotension between patients who receive a repeated amiodarone bolus dosing regimen and those who receive a conventional amiodarone bolus dosing regimen.
- Compare the incidence and severity of conduction abnormalities between patients who receive a repeated amiodarone bolus dosing regimen and in those who receive a conventional amiodarone bolus dosing regimen.
- Compare the incidence and severity of amiodarone-related pulmonary fibrosis between patients who receive a repeated amiodarone bolus dosing regimen and those who receive a conventional amiodarone bolus dosing regimen.

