10.3 Postoperative data

- Date/time of ICU admission
- Date/time of extubation

- Date/time of ICU discharge
- Date/time of hospital discharge
- Vasopressor (norepinephrine, vasopressin) use at ICU admission
- Inotrope (dopamine, epinephrine, milrinone, dobutamine) use at ICU admission
- Pacemaker use at ICU admission
- Date/time of first AF
- Presence of rapid ventricular response with first AF
- Heart rate at time of AF diagnosis
- Heart rate at initiation of study group treatment (initial amiodarone bolus)
- Hourly heart rate for 24 hours, beginning at start of study group treatment
- Date/time of study randomization
- Date/time of first study drug administration
- Total number of amiodarone boluses administered
- Restoration of normal sinus rhythm by ICU discharge
- Restoration of normal sinus rhythm by hospital discharge
- Date/time of normal sinus rhythm
- Total number of stable AF episodes (excluding initial episode) prior to ICU discharge
- Total number of stable AF episodes (excluding initial episode) prior to hospital discharge
- Presence of hypotension (SBP < 90 mmHg or increase in vasopressor infusion by 1.5x to achieve SBP > 90 mmHg) after amiodarone therapy during amiodarone IV load period
- Severity of hypotension after amiodarone therapy during amiodarone IV load period
 - Mild: No intervention needed
 - Moderate: Hypotension resolved after fluid bolus

- Severe: Hypotension requiring vasopressor or inotropic therapy
- Very Severe: Hypotension requiring multiple vasopressor or inotropic therapies
- Presence of bradycardia (HR <60 beats per minute) after amiodarone therapy during amiodarone IV load period
- Presence of conduction abnormality during amiodarone IV load period
- Severity of conduction abnormality during amiodarone IV load period
 - Mild: No intervention
 - Moderate: Temporary pacemaker required for ≤ 12 hrs
 - Severe: Temporary pacemaker required for 12-48 hrs
 - Very Severe: Temporary pacemaker required for ≥ 48 hrs or permanent pacemaker required
- Presence of pulmonary fibrosis related to amiodarone therapy
- Severity of pulmonary fibrosis related to amiodarone therapy
 - Mild: No intervention needed
 - Moderate: Discharged on oxygen at night only
 - Severe: Discharged on continuous oxygen
 - Very Severe: Discharged on mechanical ventilation or patient death due to pulmonary fibrosis

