- To compare the time to achieve NSR between patients in each group, the time to achieve NSR will be calculated for each patient. For patients who do not convert to NSR by the time they are discharged from the hospital, the date/time that they achieve NSR will be the date/time of hospital discharge. The time to achieve NSR data will be analyzed for normality. Normal data will be described by the mean and standard deviation, whereas non-normal data will be described by the median and interquartile range. If one group is normal and one group is non-normal, both groups will be reported as non-normal data. The time to achieve NSR will then compared with either the 2-tailed, independent samples student t-test (normal data) or with the Mann-Whitney U test (non-normal data).
- To compare the percentage of patients who achieve NSR by ICU discharge and hospital discharge, the number of patients in each group who have converted to NSR at each time point will be calculated and reported as number and percentage. The number who have achieved NSR will be compared with the Fischer's Exact test or the Chi-Square test, as appropriate.
- To compare the percentage of patients who have recurrent AF before ICU discharge and hospital discharge, the number of AF episodes after the initial AF episode will be counted

for each patient in each group prior to ICU discharge and prior to hospital discharge. The mean (normal data) or median (non-normal data) number of additional AF episodes will be compared between the groups using the 2-tailed, independent samples student t-test (normal data) or with the Mann-Whitney U test (non-normal data).

- To compare the incidence and severity of hypotension, the number of patients who develop hypotension will first be calculated and reported as number and percentage. The number of patients with hypotension will be compared with the Fischer's Exact test or the Chi-Square test, as appropriate . The number of patients who develop mild, moderate, severe or very severe hypotension will then be calculated and reported as number and percentage. The number of patients with each severity class will then be compared between groups using Somers' D test for ordinal data.

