- To compare the incidence and severity of conduction abnormalities, the number of patients who develop bradycardia will first be calculated and reported as number and percentage. The number of patients with bradycardia will be compared with the Fischer's Exact test or the Chi-Square test, as appropriate. The number of patients who develop mild, moderate, severe or very severe conduction abnormalities will then be calculated and reported as number and percentage. The number of patients with each severity class will then be compared between groups using Somers' D test for ordinal data.

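### The recurrent-AF objective names a percentage of patients but only episode counts are compared; as a minor companion point, conduction-abnormality incidence is tested as bradycardia

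*Protocol*

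**What the plan says.** **Recurrent AF.** Protocol section 3.2 sets the objective: "Compare the percentage of patients who have recurrent AF before ICU discharge and before hospital discharge". The matching bullet in protocol section 11.3 opens with the same percentage. It then counts each patient's further episodes and states that the average (mean if normal, otherwise median) "number of additional AF episodes will be compared between the groups using the 2-tailed, independent samples student t-test", with Mann-Whitney as the non-normal alternative. The bullet contains no percentage and no test of proportions. SAP section 1.3 repeats it. The data list in protocol section 10.3 holds the count for each discharge point; the ICU item reads "Total number of stable AF episodes (excluding initial episode) prior to ICU discharge".

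The bullet just before it, on NSR by discharge, is handled differently: patients "who have converted to NSR at each time point will be calculated and reported as number and percentage", followed by Fisher or chi-square.

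**Conduction abnormalities.** The objective in section 3.2 covers incidence and severity. For incidence, section 11.3 (and SAP 1.3) says that "the number of patients who develop bradycardia will first be calculated and reported as number and percentage", then tests that number. The severity step in the same bullet uses conduction-abnormality classes. Section 10.3 lists two separate items: "Presence of bradycardia (HR <60 beats per minute) after amiodarone therapy during amiodarone IV load period" and "Presence of conduction abnormality during amiodarone IV load period".

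**The concern.** In part (a) the plan changes variable within one bullet. Whether a patient recurs and how often a patient recurs are different quantities, and only the second is summarised and tested. A reader looking for the answer to the stated objective would not find it in the planned output. The count test also responds to episode frequency among recurrent patients, so it can show a difference where the percentages are equal, or miss one where they differ. If the choice is left open, the percentage could also be added or omitted after the data are seen.

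In part (b) the incidence test and the severity table of one bullet describe different variables. Severity grades are attached to conduction abnormality, and protocol section 21 uses those grades to define adverse and serious adverse events. The hypotension bullet shows the expected pattern: "The number of patients with hypotension will be compared with the" Fisher or chi-square test, and the same variable is then graded.

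**Working it through.** The documents give no recurrence, episode or conduction rates and no sample size calculation, so there is no planned figure to reproduce. The 30 per group comes from protocol section 11 and p<0.05 from section 11.1. All rates below are assumptions.

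**1. Which branch of the plan applies.** Episode counts with many zeros are not normal. Shapiro-Wilk, the normality test named in section 11.1, gave p<0.05 in every simulated arm checked (600 per scenario). The plan would therefore report medians and use Mann-Whitney.

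**2. What the medians show.** With 30 patients the median is 0 when at most 14 recur. With X ~ Binomial(30, p), both medians are 0 with probability P(X ≤ 14)²:
- p = 0.30: 0.983² = 0.966
- p = 0.40: 0.825² = 0.680

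Simulation gives 0.965 and 0.683.

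**3. How often the tests agree.** The simulation used 10,000 trials of 30 v 30, with recurrence Bernoulli and episodes per recurrent patient 1 + Poisson. The Monte Carlo standard error is at most √(0.25/10,000) = 0.005. Agreement means the same p<0.05 decision as Mann-Whitney.

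| Recurrence | Mean episodes per recurrent patient | Agreement, chi-square / Fisher | Share p<0.05: chi-square / Fisher / Mann-Whitney |
|---|---|---|---|
| 30% v 30% | 2 v 2 | 0.986 / 0.977 | 0.052 / 0.029 / 0.051 |
| 40% v 40% | 2 v 2 | 0.974 / 0.974 | 0.051 / 0.026 / 0.049 |
| 20% v 40% | 2 v 2 | 0.942 / 0.910 | 0.400 / 0.301 / 0.382 |
| 20% v 50% | 2 v 2 | 0.934 / 0.910 | 0.693 / 0.598 / 0.669 |
| 40% v 40% | 1 v 2 | 0.892 / 0.893 | 0.050 / 0.025 / 0.119 |
| 60% v 60% | 1 v 2 | 0.623 / 0.622 | 0.048 / 0.028 / 0.380 |
| 20% v 40% | 2 v 1 | 0.839 / 0.928 | 0.400 / 0.301 / 0.240 |

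Across all seven equal-mean scenarios run (four are shown), agreement was 93-99% for chi-square and 90-98% for Fisher. In the unequal-mean rows the Mann-Whitney results are not false positives for counts; they answer a different question.

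**4. Two constructed data sets, 30 per arm.**
- 5 patients with 3 episodes each v 13 with 1 each. The percentages are 17% v 43%: Fisher p = 0.047, uncorrected chi-square p = 0.024. For Mann-Whitney, U = 5×30 + ½×25×17 = 362.5, and 362.5/900 = 0.40, the same direction as the percentages, with p = 0.11. Medians are 0 v 0.
- 18 patients with 1 episode each v 18 with 4 each. The percentages are 60% v 60%: Fisher p = 1.00. U = 18×12 + ½×12×12 = 288, and 288/900 = 0.32, with p = 0.011. Medians are 1 v 4.

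**5. Part (b).** Its size cannot be estimated from the documents. As a constructed possibility only, bradycardia in 10/30 v 10/30 (Fisher p = 1.00) can coexist with conduction abnormality in 2/30 v 9/30 (Fisher p = 0.042).

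**The case against.** **Part (a) is mostly a reporting gap.** The tests agree in most trials unless episode frequency differs between arms, and nothing in the documents makes such a difference likely. The percentage can be derived from the collected counts at any time. This stands and limits the size of the point. It does not supply the missing quantity.

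**The spread would help the reader.** Section 11.1 describes non-normal data by median and interquartile range, so the upper quartile generally rises above 0 once more than about a quarter of an arm recur. That is fair, but quartiles still do not give the number of patients who recurred.

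**Part (b) is small.** Every graded abnormality falls in one of four classes, the lowest needing no intervention, so the incidence can be summed from the planned table. Section 11.1 also compares nominal postoperative data in general terms, although under a baseline heading, so it only arguably covers this test. In addition, the data list gives bradycardia a threshold but does not define conduction abnormality. All of this stands; what is missing is a specified incidence test on the right item.

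**A percentage has its own difficulty.** A patient who never converts has no further episode and counts as recurrence-free. The count analysis has the same feature, so this calls for a clear statement and a side-by-side display and is no reason to keep counts alone.

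**Stronger readings to avoid.** A reader might infer that the planned t-test will mislead. The plan uses it only for normal data, which these counts are very unlikely to be. A reader might also infer that the count analysis will usually reverse the conclusion, or that conduction incidence is lost. The simulations do not support the first, and the severity table contradicts the second.

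**Conclusion.** Both mismatches are in the text of the protocol and are repeated in the SAP.

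Part (a) is the main point and should be corrected: the stated analysis does not produce the quantity its objective names. The practical effect is chiefly on reporting. Both medians are 0 in about 97% of trials at 30% recurrence in each arm and 68% at 40%. The effect on the test is usually small. It becomes material only if episodes per recurrent patient differ between arms; for example, Mann-Whitney is significant in 12% of trials v 5% for chi-square at equal 40% recurrence with 1 v 2 episodes. These figures rest on assumed rates and exactly 30 per arm.

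Part (b) is minor: only the incidence test is missing, since the total can be summed from the reported classes. Neither part touches the primary analysis.

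**What to change.** **(a) Recurrent AF.** In protocol section 11.3 and SAP section 1.3:
- Calculate the number and percentage of randomised patients with at least one recurrence by ICU discharge and by hospital discharge, derived from the episode counts in section 10.3, and compare them by Fisher or chi-square.
- Keep the episode counts as supporting description.
- Show the result beside the NSR conversion percentages at the same time points, and state that patients who never converted count as having no recurrence.
- Settle the scope. Section 10.3 collects only stable episodes, while the objective and analysis say AF without that limit. Either word both as recurrent stable AF or add unstable recurrences to the data list.

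**(b) Conduction abnormalities.** Use the conduction-abnormality presence item for the incidence test, say what counts as one, and report bradycardia on its own line.

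**Cost.** One bullet each for recurrence and conduction, reworded in both documents, plus the objective in section 3.2 if recurrence is limited to stable AF. That route needs no extra data. Covering all recurrent AF needs a small extra data item. Part (b) uses items already listed.

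### Severity of hypotension and conduction abnormality is compared over four classes with no 'none' class and no stated analysis set; for conduction abnormality this may leave an excess of events untested

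*Protocol*

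**What the plan says.** Protocol 3.2 lists incidence and severity of hypotension, and incidence and severity of conduction abnormalities, among the secondary objectives.

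**Hypotension (Protocol 11.3, repeated in SAP 1.3).** Incidence comes first: "The number of patients with hypotension will be compared with the Fischer's Exact test or the Chi-Square test". Severity follows: "The number of patients who develop mild, moderate, severe or very severe hypotension will then be calculated", and then "The number of patients with each severity class will then be compared between groups using Somers' D test".

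**Conduction abnormality (same sections).** The incidence step is on a different variable: "the number of patients who develop bradycardia will first be calculated and reported as number and percentage", with a Fisher or chi-square test on that number. The severity step then uses the same four classes: "The number of patients who develop mild, moderate, severe or very severe conduction abnormalities will then be calculated", again followed by Somers' D.

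**Data collected (Protocol 10.3).** Presence and severity of hypotension are separate items. Presence is defined as "Presence of hypotension (SBP < 90 mmHg or increase in vasopressor infusion by 1.5x to achieve SBP > 90 mmHg", and the lowest severity class is "Mild: No intervention needed". Bradycardia (HR below 60), presence of a conduction abnormality and its severity are three separate items.

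Neither document says which patients enter the Somers' D calculation.

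**The concern.** In both scales the lowest class, mild, grades an event that is present and needed no intervention. A patient without the event has no class to be placed in. An analyst who follows the text would probably leave that patient's severity blank and run Somers' D on event patients alone.

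That subset is defined after randomisation, and the regimen can change who is in it: RBDR allows up to five additional boluses in 24 hours. A comparison within it is not a randomised comparison. If RBDR adds mainly mild events, its average severity among event patients falls, and the severity result can favour the arm with more harm. Another analyst could place non-events below mild, obtain the opposite sign from the same data, and also claim to have followed the plan.

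The stakes differ between the two outcomes. Hypotension has its own incidence test. Conduction abnormality as such does not, so Somers' D is the only planned between-arm test of it.

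**Working it through.** The documents give no event rate, severity mix, effect size or power for these outcomes, so there is no plan figure to reproduce. The inputs taken from the documents are 30 patients per arm (Protocol 11), the four classes (10.3 and 11.3) and significance at p < 0.05 (11.1). **All event counts and rates below are assumptions.**

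Somers' D of severity given arm = (pairs with the RBDR patient worse − pairs with the CDR patient worse) / all CDR–RBDR pairs.

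**1. One illustrative table** (none/mild/moderate/severe/very severe): CDR 24/2/2/1/1, RBDR 15/6/5/3/1. RBDR has more events (15 v 6) and more severe-or-worse events (4 v 2).

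- All 30 per arm, 'none' lowest. RBDR worse: 24×15 + 2×9 + 2×4 + 1×1 = 387. CDR worse: 2×15 + 2×21 + 1×26 + 1×29 = 127. D = (387 − 127)/900 = **+0.29**, p about 0.02.
- Event patients only (6 v 15, 90 pairs). RBDR worse: 2×9 + 2×4 + 1×1 = 27. CDR worse: 2×6 + 1×11 + 1×14 = 37. D = (27 − 37)/90 = **−0.11**, p about 0.68.
- Planned incidence test, 6/30 v 15/30: Fisher p = 0.029; uncorrected chi-square p = 0.015.

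The sign changes with the analysis set, but the negative value is noise, and the incidence test flags the excess.

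**2. Two further tables, chosen to show the range**

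| CDR | RBDR | D, all patients | D, event patients | Fisher, incidence |
|---|---|---|---|---|
| 24/2/2/1/1 | 12/6/6/3/3 | +0.40 (p = 0.0008) | 0.00 (p = 1.00) | p = 0.003 |
| 25/0/1/3/1 | 13/8/4/4/1 | +0.34 (p = 0.006) | −0.61 (p = 0.011) | p = 0.003 |

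In the second row the reversal is nominally significant, although RBDR has 17 events against 5. A rank approximation gives about 0.03 in place of 0.011, which does not change the reading.

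**3. Rejection rates.** 3,000 simulated trials per scenario, 30 per arm, CDR incidence 20%, severity mix among events 40/30/20/10% in both arms. The tie-corrected rank test supplies the p-value for Somers' D.

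| RBDR incidence | Somers' D, event patients | Somers' D, all patients | Fisher, incidence |
|---|---|---|---|
| 40% | about 5% | about 37% | about 28% |
| 50% | about 5% | about 67% | about 59% |
| 60% | about 5% | about 88% | about 86% |

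**4. A milder mix on RBDR.** Incidence 20% v 50%; mix 20/20/40/20% on CDR and 50/20/20/10% on RBDR. Severe or worse in all patients is then 0.20 × 60% = 12% v 0.50 × 30% = 15%. The event-only D favours RBDR in about 91% of trials and is significant in about 26%. The all-patient D rejects in about 55% and Fisher on incidence in about 58%.

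**5. Which planned test covers which outcome**

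| Outcome | Incidence test planned on | Severity test |
|---|---|---|
| Hypotension | presence of hypotension | Somers' D, four classes |
| Conduction abnormality | bradycardia | Somers' D, four classes |

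If Somers' D is restricted to event patients, step 3 applies to conduction abnormality without the Fisher column, unless the abnormality shows up as bradycardia.

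**The case against.** Four points can be made for the plan.

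- **The restriction is not written.** Neither document limits Somers' D to event patients. Presence is collected separately, so an analyst could place non-events below mild. This stands: what the text supports is an unstated analysis set, with event-only as the natural reading.
- **Hypotension incidence is tested first.** A reader might infer that the plan could miss an excess of hypotension. The documents do not support that. The incidence test covers all randomised patients and gives p = 0.029 in the first illustration. At an assumed 20% v 50% it has about 59% power by Fisher (about 69% by uncorrected chi-square), against about 67% for the all-patient Somers' D.
- **The 5% is not lost power.** A reader might set 67% against 5% and call the difference the cost of the plan. With the same severity mix in both arms, severity among events truly does not differ, so an event-only test should reject at about alpha. It answers another question. An incidence test followed by graded severity among events is a recognisable two-part layout; what does not stand is a between-arm test in the second part, because it conditions on a post-randomisation event.
- **The full distribution will be visible.** The number and percentage in each class are reported by arm, and severe and very severe events are handled as AE and SAE under Protocol 21. That limits the harm. It does not remove a misleading p-value or supply the missing conduction test.

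**Conclusion.** The point holds, with different weight for the two outcomes.

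For hypotension it is an ambiguity that needs one sentence. On the natural reading, the severity test can be null or favour the wrong arm while the incidence test beside it shows an excess. The likely harm is a contradictory safety message, not an undetected difference.

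For conduction abnormality the gap is larger. The only incidence test is on bradycardia, although presence of a conduction abnormality is collected. With an event-only Somers' D, an excess of conduction abnormalities would have no between-arm test, and a named part of the secondary objective would go unanswered. If non-events were included, the gap would mostly close, but the documents do not say that they are.

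The direction of the problem follows from the text. Its size depends on assumed rates and severity mixes. These are secondary safety analyses, and the primary outcome is not affected.

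**What to change.** In Protocol 11.3 and SAP 1.3, for both outcomes:

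1. State that severity is scored 0 = none, 1 = mild, 2 = moderate, 3 = severe, 4 = very severe in all randomised patients. State that Somers' D (severity given arm) is computed on this scale with a 95% CI.
2. Show the four-class breakdown among event patients as description only, with no test.
3. For conduction abnormality, add a Fisher or chi-square comparison of the number of patients with a conduction abnormality, and keep the bradycardia comparison as a separate result.

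Cost: a sentence or two in each of two bullets, one extra secondary p-value and a little analysis time. No new data are needed, because the presence items in Protocol 10.3 already supply the zero level. For hypotension the change should not be presented as a power gain over the incidence test; its purpose is a severity comparison that respects randomisation and has one possible reading.
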